## LIST OF ABBREVIATIONS

Abbreviation	Term
ADA	Anti-Drug Antibody
AE	Adverse Event
AESI	Adverse Event of Special Interest
ALP	Alkaline Phosphatase
ALT	Alanine Aminotransferase
ANCOVA	Analysis of Covariance
ANOVA	Analysis of Variance
AST	Aspartate Aminotransferase
ATC	Anatomical Therapeutic Chemical
AUC	Area under the Curve
BLQ	Below the Limit of Quantification
BMI	Body Mass Index
bpm	Beats per Minute
CI	Confidence Interval
Cmax	Maximum Concentration
CMH	Cochran-Mantel-Haenszel
CPK	Creatinine Phosphokinase
CRO	Contract Research Organization
CSR	Clinical Study Report
dL	Deciliter
DLQI	Dermatology Life Quality Index
DPS	Dynamic Pruritus Scale
ECG	Electrocardiogram
eCRF	electronic Case Report Forms
EMA	European Medicines Agency
FDA	Food and Drug Administration
GGT	Gamma-Glutamyl Transpeptidase
HDL	High-Density Lipoprotein

Abbreviation	Term
hsCRP	High Sensitivity C-Reactive Protein
ICF	Informed Consent Form
ICH	International Conference on Harmonisation
IGA	Investigator's Global Assessment
IgE	Immunoglobulin E
IL	Interleukin
IRR	Injection-related Reaction
ITT	Intent-to-treat; intention-to-treat
IVRS	Interactive Voice Response System
IWRS	Interactive Web Response System
KM	Kaplan-Meier
LDH	Lactate Dehydrogenase
LDL	Low-Density Lipoprotein
LOCF	Last Observation Carried Forward
LSmean	Least Squares Mean
MCV	Mean Cell Volume
MedDRA	Medical Dictionary for Regulatory Activities
MI	Multiple Imputation
mL	Milliliter
NCA	Non-Compartmental Analysis
NRS	Numeric Rating Scale
OC	Observed Case
PAS	Prurigo Activity Score
PCSV	Potentially Clinically Significant Value
PD	Pharmacodynamics
PDAP	PD Analysis Population
PEF	Peak Expiratory Flow
PK	Pharmacokinetics
PKAP	PK Analysis Population
PN	Prurigo nodularis

Abbreviation	Term
PP	Per-Protocol
PT	Preferred Term
Q1	Lower quartile
Q3	Upper quartile
Q4W	Every 4 weeks
QoL	Quality of Life
RA	receptor A
RBC	Red Blood Cell
ROC	Receiver Operating Characteristic
SAE	Serious Adverse Event
SAF	Safety (analysis population)
SAP	Statistical Analysis Plan
SD	Standard Deviation
SOC	System Organ Class
TARC	thymus and activation-regulated chemokine
TCS	Topical Corticosteroids
TEAE	Treatment-emergent Adverse Event
TESAE	Treatment-emergent Serious Adverse Event
TLF	Tables, Listings, and Figures
ULN	Upper Limit of Normal
VRS	Verbal Rating Scale
WBC	White Blood Cell
WHODD	World Health Organization Drug Dictionary

## 1 AMENDMENTS FROM PREVIOUS VERSION(S)

The following is a change from the Statistical Analysis Plan (SAP) dated 17Aug2018:

- Added details of how to calculate pharmacokinetic parameters to the section 3.2.4 of the Version 1.0 of the SAP. The new section is 5.9.1 of this Amendment of the SAP (Version 2.0).

## 2 INTRODUCTION

This SAP describes the planned analysis and reporting for GALDERMA R&D, SNC, protocol RD.03.SPR.115828, entitled “A study to assess the safety and efficacy of nemolizumab (CD14152) in subjects with prurigo nodularis (PN)”, All Countries Amendment Version 2.0 dated Apr 09, 2018.

Prurigo nodularis (PN) is characterized by the presence of symmetrically distributed multiple (up to hundreds), highly pruritic, hyperkeratotic, erosive or crusted nodules and papules (Hyde JN et al., 1909). This leads to an impaired quality of life and high burden due not only to the severe itch but also the chronic, skin lesions and lack of treatment options (Warlich B., et al 2015).

The goal of PN treatment is to break the itch-scratch cycle and allow the skin to heal. Treatment of chronic pruritus is still notoriously challenging and frustrating for both dermatologists and patients as in the majority of cases, the response is either limited or associated with severe adverse events with the current therapy options. There is no standardized or approved therapy for PN up-to-date and evidence from controlled studies is limited (Fostini AC et al., 2013). The difficulty in treating this disease is reflected in the wide range of treatments proposed in the literature.

Nemolizumab (CD14152) is a humanized anti-human IL-31 receptor A (RA) monoclonal antibody that inhibits the binding of IL-31 to IL-31RA and subsequent signal transduction. IL-31 has been suggested to be a key player in the development of pruritus. Recent clinical studies of nemolizumab in patients with atopic dermatitis showed a rapid onset of pruritus reduction within one week followed by disease improvement (Ruzicka T et al 2017).

The main objective of this study is to evaluate the efficacy, safety and pharmacokinetics (PK) of multiple subcutaneous doses of nemolizumab in the treatment of pruritus and lesions associated to PN.

The planned analyses identified in this SAP may be included in the clinical study report (CSR), regulatory submissions, or future manuscripts. Also, post hoc exploratory analyses not necessarily identified in this SAP may be performed to further examine study data. Any post hoc, or unplanned, exploratory analyses performed, if included, will be clearly identified as such in the final CSR.

This SAP is based upon the following study documents:

- Study protocol, All Countries Amendment Version 2.0 (09 Apr 2018)
- Electronic Case Report Form (eCRF), Version 6.0 (11-June-2018).

The structure and content of this SAP provides sufficient detail to meet the requirements identified by the Food and Drug Administration (FDA), European Medicines Agency (EMA), and International Conference on Harmonisation (ICH) of Technical Requirements for Registration of Pharmaceuticals for Human Use: Guidance on Statistical Principles in Clinical Trials. All work planned and reported for this SAP will follow internationally accepted guidelines, e.g., Ethical Guidelines for Statistical Practice published by the American Statistical Association and Code of Conduct published by the Royal Statistical Society, for statistical practice.

The reader of this SAP is encouraged to also read the clinical protocol, and other relevant documents for details on the planned conduct of this study. Other than the schedule of assessments which is provided in Appendix 1, operational aspects related to collection and timing of planned clinical assessments are not repeated in this SAP unless relevant to the planned analyses.

### **3 STUDY OBJECTIVES**

#### **3.1 Primary Objective**

The primary objective is to assess the efficacy of nemolizumab compared to placebo in the treatment of pruritus in patients suffering from PN.

#### **3.2 Secondary Objectives**

The secondary objectives are:

Efficacy and safety:

- Evaluation of the safety of nemolizumab compared to its placebo in patients with PN.

- Evaluation of the efficacy of nemolizumab compared to its placebo in the treatment of *prurigo* lesions in patients with PN.
- Evaluation of nemolizumab effect compared to its placebo on quality of life in patients with PN

#### Pharmacokinetics (PK)

- Characterization of nemolizumab PK profile and exposure response relationship in patients with PN

#### Pharmacodynamics (PD)

- Evaluation of the effect of nemolizumab on biomarkers in patients with PN

#### Biophysical

- Evaluation of the efficacy of nemolizumab on scratching events and sleep improvement using actigraphy
- Evaluation of the efficacy of nemolizumab on lesions improvement using whole body images device only on equipped sites. This will be evaluated based on the availability of the data.

## 4 INVESTIGATIONAL PLAN

### 4.1 Overall Study Design and Plan

This is a randomized, placebo-controlled, double-blinded, parallel group, multicenter study to evaluate the safety and efficacy of nemolizumab in patients suffering from PN. Approximately 70 adult patients suffering from PN for at least 6 months with severe pruritus defined by the mean of the worst daily intensity of the NRS score  $\geq 7$  over the previous week at baseline will be randomized in the study. Subjects meeting inclusion/exclusion criteria will be randomized in a 1:1 ratio to nemolizumab or placebo. Each subject will receive three subcutaneous injections of 0.5mg/kg of nemolizumab or matching placebo. Injections will be administered every 4 weeks (at baseline, week 4 & week 8).

Subjects' participation in the study will be up to 22 weeks, including an up to 4-week screening period, a 12-week treatment period (last study drug injection at week 8) and a 6-week follow-up period (10 weeks after the last study drug injection corresponding to 5 half-lives of nemolizumab).

Assessments of efficacy, safety, PK, PD, and biophysical will be conducted throughout this clinical trial. Refer to Appendix 1 for the complete schedule of assessments.

## 4.2 Efficacy and Safety Variables

### 4.2.1 Efficacy Variables

#### 4.2.1.1 Pruritus Numeric Rating Scale (NRS)

Pruritus NRS is a scale to be used by the subjects to report the intensity of their pruritus (itch) during the last 24 hours all along the study from first screening visit to the follow-up visit. Subjects will receive instructions on how to record their pruritus NRS scores on an electronic device and will complete the assessment once daily at home in the evening throughout the clinical trial (including the follow-up period).

Subjects will be asked the following questions in their local language:

- For average itch intensity: “On a scale of 0 to 10, with 0 being ‘no itch’ and 10 being ‘worst itch imaginable’, how would you rate your itch overall during the previous 24 hours?”
- For maximum (Peak) itch intensity: “On a scale of 0 to 10, with 0 being ‘no itch’ and 10 being ‘worst itch imaginable’, how would you rate your itch at the worst moment during the previous 24 hours?”

Weekly prorated average score will be calculated and used in the analysis. If a subject has less than 5 diary entries in a week, the weekly average scores will be set to missing. Refer to Section 5.2 for classification of diary data into analysis week/visit.

#### 4.2.1.2 Verbal Rating Scale (VRS)

The VRS consists of a list of adjectives describing different levels of symptom intensity, to be used by the subjects to report the intensity of their pruritus (itch) over the last 24 hours. Subjects will receive instructions on how to record their pruritus VRS scores on an electronic device and will complete the assessment once daily in the evening from Screening visit 2 and throughout the clinical trial (including the follow-up period). In the eDiary, patients will mark on a 5-point VRS, the response that best describes their pruritus intensity in the last 24 hours.

Subjects will be asked the following questions in their local language:

- For average itch intensity: “On a scale of 0 to 4, with 0 being ‘no itch’ and 4 being ‘very severe itch’, how would you rate your itch overall during the previous 24 hours?”
- For maximum (Peak) itch intensity: “On a scale of 0 to 4, with 0 being ‘no itch’ and 4 being ‘very severe itch’, how would you rate your worst itch during the previous 24 hours?”

Weekly prorated average score will be calculated and used in the analysis. If a subject has less than 5 diary entries in a week, the weekly average scores will be set to missing. Refer to Section 5.2 for classification of diary data into analysis week/visit.

#### 4.2.1.3 Dynamic Pruritus Score (DPS)

The 9-point DPS is a dynamic scale to be used by subjects to evaluate the change of their pruritus compared with an earlier time point (i.e. before injection on Day 1). The scale ranges from 0 (strongly worsened pruritus) to 8 ([almost] no pruritus anymore), including intermediate marks for slightly improved/worsened, moderately improved/worsened, and rather improved/worsened. Subjects will receive instructions on how to record their DPS score on an electronic device displaying the scale in their local language, and will complete the assessment 24, 48h and 72h after the 1st injection at baseline and at W4 before the second injection. This assessment will be performed by the subject based on his itch perception over the 24h hours preceding the baseline injection.

#### 4.2.1.4 Investigator Global Assessment of Prurigo (IGA)

IGA is a 5-point scale ranging from 0 (clear) to 4 (severe) used by the investigator or trained designee to evaluate the severity of the disease. IGA corresponds to the overall assessment of the severity of prurigo including presence of crust and nodules or skin bleeding that will be evaluated at Baseline, Week 4, Week 8, Week 12, Week 18 & in case of Early termination visit / Unscheduled visit, if applicable.

#### 4.2.1.5 Assessment of Prurigo Activity Score (PAS)

The evaluation of the disease will be performed by the Investigator using the Prurigo Assessment Scale (PAS) at baseline and Week 12 using the entire scale and at Weeks 4, 8, 18 and in case of Early termination visit / Unscheduled visit, if applicable using item 5 (number of lesions only) and 6 (excoriation/crusts and healed lesions).

#### 4.2.1.6 Sleep Disturbance Numeric Rating Scale (NRS)

The sleep disturbance NRS is a scale to be used by the subjects to report the degree of their sleep loss related to PN. Subjects will receive instructions on how to record their sleep disturbance NRS scores on an electronic device and will complete the assessment once daily in the morning from Screening 2 (Day - 7) to Week 4 visit (Day 29).

Subjects will be asked the following question in their local language:

On a scale of 0 to 10, with 0 being 'no sleep loss related to signs/symptoms of PN' and 10 being 'I cannot sleep at all due to the signs/symptoms of PN', how would you rate your sleep last night?"

Weekly prorated average score will be calculated and used in the analysis. If a subject has less than 5 diary entries in a week, the weekly average scores will be set to missing. Refer to Section 5.2 for classification of diary data into analysis week/visit.

#### 4.2.1.7 Dermatology Life Quality Index (DLQI)

DLQI is a validated 10-item questionnaire, covering domains including symptoms/feelings, daily activities, leisure, work/school, personal relationships and treatment. Subject will rate each question ranging from 0 (not at all) to 3 (very much), and the total score ranges from 0 to 30, with a higher score indicating a poorer quality of life. Please note that "Not relevant" is scored as 0, and Question 7 'Yes – prevented working or studying' is scored as 3. DLQI will be given only to the subset of subjects who fluently speak a language in which the questionnaire is presented (based on availability of validated translations in participating countries). This assessment will be performed by the subject on the provided electronic device at baseline, Week 4, and Week 12, and in case of Early termination visit / Unscheduled visit, if applicable.

For general inflammatory skin conditions, a change in DLQI score of at least 4 points is considered clinically important. Refer to Appendix 3 for details on scoring, data handling rules, and analysis on DLQI.

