1 BACKGROUND AND RATIONALE

1.1 Medical background and Short rationale for the clinical trial

Prurigo nodularis (PN) is characterized by the presence of symmetrically distributed multiple (up to hundreds), highly pruritic, hyperkeratotic, erosive or crusted nodules and papules (Hyde JN et al., 1909). This leads to an impaired quality of life and high burden due not only to the severe itch but also the chronic, skin lesions and lack of treatment options (Warlich B., et al 2015).

No reliable data exist about incidence and prevalence of PN in the general population, but it seems to be more frequent and intense in females and elderly (Iking A., et al., 2013).

The physiopathology of PN is still not fully understood; however, the interactions between cutaneous nerve fibres, neuropeptides and immune cells seem to play an important role in the onset of PN (Zeidler C et al. 2016). It was assumed that PN is a subclinical small fibre neuropathy based on the observed reduction of intraepidermal nerve fibre density in patients' biopsies (Bharati et al 2007, Schuhknecht B et al., 2011) and observations with positive response to gabapentin and pregabalin commonly utilized in the treatment of pain and neuropathy [(Fostini et al., 2013). Changes in the morphology of skin nerve fibers with increased dermal neural hyperplasia and inflammation caused by T lymphocytes, eosinophilic, granulocytes and mast cells were described in the development and chronification of PN (Zeidler C et al., 2016).

Recent findings suggest that PN might be a consequence of chronic itch inducing neural sensitization followed by lesion appearance and development of a chronic itch-scratch cycle. A large spectrum of underlying conditions were considered as the origin of chronic pruritus classified in dermatological (e.g. atopic dermatitis), systemic (e.g. chronic kidney failure), neurological (e.g. brachioradial pruritus), psychiatric and mixed origin (Ständer S et al., 2007).

Only few studies have described the incidence and the strength of association of different comorbidities in representative cohort of patients with PN (Iking et al., 2013). An atopic predisposition seemed to be most commonly associated to PN patients in nearly half of the subjects. The atopic diathesis was also found to predict a significantly earlier age of onset (median age 19 years) compared to non-atopic patients (median age 48 years) (Tanaka et al.1995).

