PP and ITT (Criteria will be set to missing after rescue medication is used and imputed to LOCF, for continuous outcomes and to failure for binary outcomes) will be conducted on secondary endpoints.

DLQI data will be analyzed on observed cases by CMH test test stratified by background of atopy and by country with the ridit transformation and the row mean difference statistic (FREQ procedure from SAS) on the data in categories and also in terms change from baseline via an

ANCOVA including treatment, baseline DLQI as a covariate, background of atopy and country as cofactors

The absolute and the percent change in weekly average sleep disturbance NRS from baseline up to week 4 will be analyzed by CMH test stratified by background of atopy and by country with the ridit transformation and the row mean difference statistic (FREQ procedure from SAS)

The PD parameters will be visualized by boxplots (with a logarithm base 10 Y axis where needed). The compound effect will be estimated by Student's t test comparing the change at D85 from D1 for CD14152 vs the change at D85 from D1 for placebo (or other if more appropriate). The multiple testing problem will be taken into account by the Benjamini-Hochberg approach (1995)(or other if more appropriate).

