**Binary endpoints:**

All missing values will be treated as a Non-Responder for the binary endpoints. If a subject withdraws from the study, all assessments after withdrawal will be considered as Non-Responder.

- LOCF, OC, MI under missing not at random assumption approaches will be used as sensitivity analysis to impute the missing values for the selected secondary endpoints as appropriate. For sensitivity analyses, binary endpoints will be analysed using a Cochran-Mantel-Haenszel (CMH) test stratified by, presence or absence of background of atopy and country (Australia, France, Germany, Poland, and US)

There will be no imputation for missing laboratory and vital sign data.

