#### **5.7.4 Other Efficacy Endpoints**

##### **Dermatology Life Quality Index (DLQI)**

DLQI will be assessed at baseline, weeks 4, 12, or early termination visit when applicable.

The DLQI score will be categorized as follows:

- 0-1 = no effect at all on subject's life
- 2-5 = small effect on subject's life
- 6-10 = moderate effect on subject's life
- 11-20 = very large effect on subject's life
- 21-30 = extremely large effect on subject's life

The DLQI can be analyzed under 6 sub-scales, namely, symptoms and feelings (question 1 and 2), daily activities (question 3 and 4), leisure (question 5 and 6), work and school (question 7), personal relationships (question 8 and 9), and treatment (question 10). For general inflammatory skin conditions, a change in DLQI score of at least 4 points is considered clinically important.

The primary study population for all QoL and productivity data will be the ITT Population. DLQI will be summarized by treatment group and visit. By-subject listings of these data should be provided.

Change from baseline in DLQI at each visit will be analyzed using ANCOVA with treatment group, baseline DLQI as a covariate, background of atopy and country as cofactors. In addition, the following analyses will be performed:

- A shift table (by visit) will be generated using the categories described above. Change from baseline in each sub-scale at each visit will be analyzed as the efficacy endpoint using ANCOVA.
- Proportion of subjects achieving a change in DLQI score of at least 4 points at each Visit up to week 12 will be analyzed using a CMH test with ridit scores between nemolizumab and placebo, stratified by background of atopy (presence or absence) and country.

Number and percentage of subjects will also be provided for the following DLQI score categories at each visit for the above categories and analyze using CMH test stratified by background of atopy and by country with the ridit scores.

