#### Minimal Clinically Important Difference of the DLQI

For **general inflammatory skin conditions** a change in DLQI score of at least 4 points is considered clinically important (Basra et al, 2015). This means that a subject's DLQI score has to either increase or decrease by at least 4 points in order to suggest that there has actually been a meaningful change in that subject's quality of life since the prior measurement of his/her DLQI scores (Refer to Basra MK et al. paper).

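### The DLQI 4-point responder analysis sets no baseline minimum, so subjects starting at 0-3 cannot register a 4-point improvement (minor, cheap to fix)

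*SAP*

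**What the plan says.** - **Scale.** SAP 4.2.1.7: "the total score ranges from 0 to 30, with a higher score indicating a poorer quality of life". An item marked as not relevant scores 0, and under SAP Appendix 3 so does a single unanswered item.
- **Threshold.** SAP 4.2.1.7: "For general inflammatory skin conditions, a change in DLQI score of at least 4 points is considered clinically important". SAP Appendix 3 explains that a subject's "DLQI score has to either increase or decrease by at least 4 points" to suggest a meaningful change.
- **Analysis.** SAP 5.7.4 plans a CMH test, stratified by atopy and country, of the "Proportion of subjects achieving a change in DLQI score of at least 4 points at each Visit up to week 12". On population it says: "The primary study population for all QoL and productivity data will be the ITT Population". It names neither a direction nor a baseline minimum.
- **Entry.** Protocol 5.3 sets severity by itch (weekly mean worst NRS of at least 7 at baseline), nodule count and disease duration. No criterion uses DLQI.
- **Standing of the endpoint.** Quality of life is a secondary objective (Protocol 2.1.2, SAP 3.2), but DLQI is listed among the other endpoints (Protocol 9.1.5, SAP 4.2.2.3). The 4-point proportion appears only in SAP 5.7.4. Protocol 9.2.4 plans score categories and change from baseline: "DLQI data will be analyzed on observed cases by CMH test".

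**The concern.** A responder proportion is normally read as the share of patients who benefited. A subject whose baseline DLQI is 0, 1, 2 or 3 cannot contribute to that numerator in either arm, whatever the drug does, yet remains in the denominator. If response means improvement, both rates and their difference shrink and the test loses power. If any change counts, the same subject can be scored as achieving the endpoint only by deteriorating. On neither reading can the subject show benefit.

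This is the only responder analysis serving the quality-of-life objective, and a responder rate is easily quoted on its own. At stake is how well that one number reflects the treatment effect. The primary analysis is not involved.

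**Working it through.** **The plan's own figure.** No responder rate, baseline distribution or power is stated for DLQI. The 35 per arm comes from the primary endpoint (SAP 5.10). With a difference of 30, SD 35, two-sided 5% and 90% power, the normal approximation gives 2 x (1.960 + 1.282)^2 / 0.857^2 = 28.6, so 29. The t-based calculation gives 29.6, so 30 as stated. That calculation is unaffected.

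**The floor.** The minimum is 0. A fall of 4 needs a baseline of at least 4, so baselines 0-3 are excluded from improvement by construction.

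**Dilution if response means improvement.** Let f be the share of each arm with baseline 0-3, and p1 and p0 the response rates among those with baseline of at least 4. Observed rates are p1(1-f) and p0(1-f), so the observed difference is (1-f)(p1 - p0).

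**Power.** Unstratified normal approximation, two-sided 5%: power = Phi[(d - 1.96 x SE0)/SE1], where SE0 uses the pooled rate and SE1 the separate rates. The whole-population analysis has 35 per arm with diluted rates; the restricted one has 35(1-f) per arm with rates p1 and p0.

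Assumptions, none from the documents: p1 = 70%, p0 = 35%, and the values of f. All 35 per arm are taken to have a scored DLQI.

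Example, one subject per arm (f = 1/35 = 2.9%): rates 70 x 34/35 = 68.0% and 35 x 34/35 = 34.0%; d = 0.340; SE0 = sqrt(0.51 x 0.49 x 2/35) = 0.1195; SE1 = sqrt((0.68 x 0.32 + 0.34 x 0.66)/35) = 0.1124; (0.340 - 0.2342)/0.1124 = 0.94; power 82.7%.

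| f | Difference, all (points) | Power, all | Power, baseline of at least 4 |
|---|---|---|---|
| 0 | 35.0 | 85.0% | 85.0% |
| 2.9% | 34.0 | 82.7% | 84.0% |
| 5% | 33.25 | 80.8% | 83.1% |
| 10% | 31.5 | 76.3% | 81.0% |
| 15% | 29.75 | 71.6% | 78.6% |

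Assuming 70% v 40% instead gives the same pattern: at f = 5%, 28.5 points instead of 30 and power of 67.2% v 70.0% restricted; at f = 10%, 27.0 points and 62.2% v 67.5%.

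**If any change counts.** Assume improvement of 70% v 40% among those able to improve, and worsening of 5% v 15% among low-baseline subjects only, with f = 10%. The difference is 0.9 x 30 + 0.1 x (5 - 15) = 26.0 points. If worsening of 5% v 15% is counted across the whole population, the rates are 75% v 55%, a 20-point difference instead of 30. The undefined direction can therefore matter more than the floor, so a baseline restriction alone would not be enough.

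**How large might f be?** DLQI question 1 asks about itch, soreness, pain or stinging, and the questionnaire in the protocol shows no not-relevant option for questions 1 and 2. If a subject with worst itch of at least 7 scores 2 or 3 on question 1 (an inference), a total of at most 3 leaves only 3 - 2 = 1 or 3 - 3 = 0 points over the other nine questions. That points to a small f. Not-relevant items and one unanswered item still score 0, so f need not be zero.

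**The case against.** The strongest reply is that nothing is biased. The ITT proportion correctly answers how many randomized subjects reach the threshold, and restricting it changes the target population. Any dilution acts on both arms, does not inflate type I error and does not favor nemolizumab. This stands, and it is why the point is an improvement and not an error.

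The likely size is also slight. At one subject per arm, restriction recovers 84.0 - 82.7 = 1.3 points of power in an analysis that was never powered. Protocol 1.1 says of the disease that "it seems to be more frequent and intense in females and elderly"; the mention of intensity argues against low baselines at least as much as older age argues for them. SAP 5.7.4 also keeps a baseline-adjusted ANCOVA on change, subscale ANCOVAs, score categories and a shift table. All of this stands.

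Two stronger readings are tempting, and the documents support neither:

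- A reader might infer that low-baseline subjects automatically fail in both arms under the SAP. SAP 5.7.4 speaks of change, and Appendix 3 allows either direction, so a subject going from 3 to 7 meets the literal wording. The automatic failure follows only if response means improvement.
- A reader might link the floor to the missing-data rule in SAP 5.7.1.3, "All missing values will be treated as a Non-Responder for the binary endpoints". Floor subjects have observed scores, so that rule does not create or worsen the problem.

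**Conclusion.** The point holds as a minor improvement. The omission is certain: no baseline minimum, a floor at 0 and no DLQI entry criterion mean that a subject starting at 0-3 can never show a 4-point benefit. The consequence depends on f, which the documents do not give and which is probably small. Under the assumed 70% v 35%, the loss is 1.0 point of difference at one subject per arm, 1.75 points at f = 5% and 3.5 points at f = 10%. The power forgone by not restricting is 1.3, 2.3 and 4.7 points respectively, and nothing is lost at f = 0. The power figures ignore the CMH stratification and assume every subject has a DLQI score.

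The effect is conservative and confined to one analysis of an unpowered endpoint without multiplicity control. A reader should not infer that the trial's quality-of-life conclusion is at risk, because the baseline-adjusted analysis of change does not use the threshold.

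**What to change.** In SAP 5.7.4:

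1. Define a DLQI responder as a subject whose score decreases by at least 4 points from baseline. The restriction below does not work without this.
2. Analyse that endpoint in ITT subjects with baseline DLQI of at least 4, and report the number excluded per arm. Protocol 8.1.2.1 has the DLQI completed before the first injection, so selecting on it keeps the comparison randomized.
3. Optionally show the all-ITT proportion as supportive.
4. Keep the change-from-baseline ANCOVA on all subjects.

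The cost is a sentence or two in the SAP and a slightly smaller denominator for this one analysis, whose result then applies to subjects able to respond and not to everyone randomized.
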